### **Assessment of Contraindications**

Use of cilostazol will be additionally evaluated for the use in patients with diseases and conditions listed as contraindications in the SmPC. These contraindications are the following:

- Severe renal impairment
- Moderate to severe hepatic impairment
- Congestive heart failure
- History of bleeding disorders: active peptic ulcer, recent haemorrhagic stroke, proliferative diabetic retinopathy, poorly controlled hypertension
- History of arrhythmias: ventricular tachycardia, ventricular fibrillation or multifocal ventricular ectopics, prolongation of the QT interval

The diagnosis codes that will be used to define the variables for the evaluation of contraindications are included in Table 4.

### **Overall Assessment of Contraindications**

Overall assessment will be conducted by evaluating the number of users who are current smokers at the start date, have a labelled contraindication for the use of cilostazol, or have a new 2013 SmPC contraindication.

### **9.3.7 Indications Associated With Treatment and Off-Label Prescribing**

Indication for the initiation of treatment with cilostazol and off-label use will be assessed according to the type of data available in each database. In most databases, the indication for which the treatment is given is not recorded as a separate field and must

be assessed by diagnosis codes recorded around the date of the first cilostazol prescription and by manual review of the computerised clinical information including free-text comments from the prescriber, when these are available (e.g., THIN).

Because of these limitations, the indication associated with cilostazol treatment and off-label prescribing of cilostazol at the start date will be assessed in a random sample of about 200 patients in databases with available primary care diagnosis. The computerised information from these patients, including free-text comments (THIN), will be manually reviewed to assess the indication and off-label prescribing of cilostazol. The random sample will be identified using simple random sampling stratified by age (< 70 years and ≥ 70 years) and strength of first prescription (50 mg and 100 mg).

For databases that do not have free-text comments or those with only hospital discharge diagnoses, indications for cilostazol will be evaluated by hospital discharge diagnoses.

The definition of off-label use of cilostazol will be based on diagnoses for a disease or medical condition other than the labelled indications in the SmPC. In the absence of labelled indications, potential off-label use may include, among others, prevention of secondary stroke and prevention of ischaemic heart disease.

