*Indications associated with treatment and off-label prescribing:* In most databases, the indication for which the treatment is given is not recorded as a separate field and must be assessed by diagnosis codes recorded around the date of the first cilostazol prescription and/or by manual review of the computerised clinical information, including free-text comments from the prescriber when these are available (e.g., THIN). Because review of computerised information is very time- and resource consuming, the indication associated with cilostazol treatment and off-label prescribing of cilostazol in THIN will be assessed in a random sample of about 200 patients stratified by age and strength of first prescription of cilostazol. For the rest of databases, which do not have free-text comments, indications for cilostazol will be evaluated for all patients by hospital discharge diagnoses.

*Assessment of hospitalisations during treatment with cilostazol:* The percentage of users of cilostazol who are hospitalised for any cause during treatment will be assessed.

*Speciality of prescribers:* The type of prescriber initiating treatment with cilostazol will be ascertained in the databases that have this information available: IACS, SIDIAP, GePaRD, Sweden.

**Data sources:** The study is proposed to be conducted in the following databases:

- The Aragón Health Sciences Institute (Instituto Aragonés de Ciencias de la Salud [IACS]) database, Spain
- The Information System for the Advancement of Research in Primary Care (Sistema d'Informació per el Desenvolupament de la Investigació en Atenció Primària [SIDIAP]) database in Catalonia, Spain
- The German Pharmacoepidemiological Research Database (GePaRD), Germany. Conduct of the study in the GePaRD needs approval by the statutory health insurance providers (SHIs)
- The Health Improvement Network (THIN), United Kingdom (UK)
- The Swedish National Registers

**Study size:** We ascertained the preliminary number of new users of cilostazol in SIDIAP, THIN, and Swedish databases. For GePaRD, we estimated the number of new users in the database based on the reported use of cilostazol in Germany. For IACS in Spain, the number of new users is yet to be ascertained. Overall, the estimated total number of new users in the study databases is between 11,000 and 17,000 (pending the number of new users from IACS and confirmation from GePaRD and Sweden).

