**Data analysis:** The use and patterns of use of cilostazol will be summarised by the total number of users, prescriptions, and number of defined daily doses (DDDs), and by the number of users according to daily dose and duration of use. Characteristics of users, comorbidity, comedications, use of interacting drugs, and conditions defined for the evaluation of risk minimisation measures, contraindications, indications, off-label use, hospitalisations, and prescriber speciality will be described as number and percentage of patients with each condition. All analysis will be stratified by age and sex. Shell tables of results for the planned analysis are presented in a separate file (Cilostazol shell analysis tables Final.xlsx).

**Limitations:** Drug utilisation studies conducted in automated health databases allow identification of patients who are prescribed or dispensed the drugs of interest and characterisation of these patients according to prior medical history, use of medications, and patterns of use of medications. Health care databases have become a standard tool for conducting research to study the safety of drugs as information on diagnoses and treatments is recorded on an ongoing basis. Thus, the proposed DUS will comply with the request of the Rapporteur Assessment (Joint Assessment Report, July 2012) to provide data on the use of cilostazol across several populations in Europe.

This study will address all the requirements with the exception of three components of the evaluation of risk minimisation measures: (1) smoking status and history, which is only partially available in THIN and GePaRD; (2) assessment of physical exercise, which is not recorded in the study databases; and (3) ascertainment of the indication of cilostazol (no direct indication information is available). For the indication, we will use proxy data (i.e., diagnosis around the date of prescriptions of cilostazol) in all populations and complemented with the clinical review of the full computerised information in the UK and, if possible, in Germany.

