Drug dictionary codes/ therapeutic classification	ATC	ATC	ATC	Multilex/British National Formulary	ATC
Clinical indication	Not specifically recorded but based on proxies	Not specifically recorded but based on proxies	Not specifically recorded but based on proxies	Associated with new courses of medications, but completeness is variable Computerised free-text information is available for review	Not specifically recorded but based on proxies
Primary care diagnosis	Yes	Yes	Yes Since January 2004	Yes	No. Diagnoses from outpatient hospital clinics are available
Hospital diagnosis	Yes	Yes (CMBD-AH)	Yes	Recorded by GPs	Yes
Recorded by primary care physicians	No	No	No	Yes	No
Available from hospital database or hospital claims	Yes CMBD-AH	Yes CMBD-AH	Yes	Partial linkage to HES	Yes

Database and Size of Population Size of the Country					
Feature	IACS, Aragón, Spain (N = 1,346,293) a	SIDIAP, Catalonia, Spain (N = 7,565,603) b	German Pharmacoepidemiological Research Database (GePaRD) (N = 81,751,602) c	THIN, United Kingdom (N = 62,435,709) c	Swedish Prescription and Inpatient National Databases (N = 9,415,570) c
Disease and procedure codes	Primary health care: ICPC Hospital: ICD-9	ICD-10-CM	ICD-10-GM	Read codes	ICD-10-CM
Lifestyle risk factors	No	Yes	No	Yes	No
Data availability	Partial since 2005; Complete since 2010	Since 2006	Since 2004	Since 1980	Since July 2005
Approximate time lag (updates)	1 year	1 year	1.5 years	6 months	2012 data will be available in 3-4Q 2013
Approval process for database research	Data application and ethics committee approval required	Data application and ethics committee approval required	Approvals by SHI and Health Ministry are required	Ethics or scientific approval is required	Data application and ethics committee approval required

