Regarding the recording of clinical information, databases based on electronic medical records (e.g., THIN) usually provide data on findings of physical examinations and results of diagnostic tests. Health habits (e.g., smoking, use of alcohol) are usually recorded, at least partially, in these databases. In other databases, clinical information is restricted to clinical diagnoses such as hospital discharge diagnoses, and health habits are not recorded. For the conduct of this DUS, smoking can be partially assessed in THIN and GePaRD. Regarding the indication of treatment and off-label use, this can be evaluated in the THIN database by manual review of computerised information and free-text comments. General practitioners in the UK usually record the indication for new treatments although the recording may be incomplete. In the other study databases, the assessment of treatment indication and off-label use will be approximated by looking at diagnosis codes and use of medications before and at the start date.

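### The protocol takes indication and off-label status outside THIN from hospital discharge diagnoses although most of those databases hold outpatient diagnoses, and it states different rules elsewhere

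*Protocol*

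**What the plan says.** Two places define how indication is obtained where no free text exists. The Abstract (Variables) states: "For the rest of databases, which do not have free-text comments, indications for cilostazol will be evaluated for all patients by hospital discharge diagnoses". Section 9.3.7 sets the same source for any database that lacks free text or holds discharge diagnoses alone; there, "indications for cilostazol will be evaluated by hospital discharge diagnoses". The second sentence joins two conditions with *or*, so it covers a database that holds primary care diagnoses but no free text. Table 9 mentions reviewable free text for THIN only.

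Three other places read differently:

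- Section 9.3.7 itself, one paragraph earlier, says that indication and off-label prescribing "will be assessed in a random sample of about 200 patients in databases with available primary care diagnosis". The Abstract places this sample in THIN.
- The Abstract's Limitations paragraph promises proxy data, described as "diagnosis around the date of prescriptions of cilostazol", in all populations, with clinical review added in the UK and, if possible, in Germany.
- Section 9.9 says that indication and off-label use in the other databases will be "approximated by looking at diagnosis codes and use of medications before and at the start date", with no restriction to hospital codes.

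Section 9.3.7 bases off-label use on diagnoses other than the labelled indication. Where no labelled indication is found, it names secondary stroke prevention and prevention of ischaemic heart disease as possible off-label uses. Section 8 makes off-label prescribing a secondary objective, and section 9.7.8 reports it with 95% confidence intervals in Analysis Table 21.

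**The concern.** The two places that define the variable use a narrower source than the databases offer. The Table 9 row "Primary care diagnosis" is answered yes for IACS, SIDIAP and GePaRD (GePaRD since January 2004). For Sweden the answer is no, but outpatient hospital clinic diagnoses are available. Section 9.3.3 already draws on primary care and hospital codes for comorbidity, and the protocol gives no reason for the narrower source here.

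The off-label definition depends on whether a labelled indication is found, so the choice of source affects the result directly. A labelled code that is never consulted looks absent. The user then becomes unknown, or potentially off-label if another candidate condition was coded at discharge.

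Three things are at stake: the off-label percentage itself; the meaning of its confidence interval, which carries sampling error but not classification error; and the DUS1 to DUS2 comparison, if different sites or phases follow different sentences of the same protocol.

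**Working it through.** **1. The rules side by side**

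| Place in Protocol | Databases | Source of indication |
|---|---|---|
| Abstract, Variables | all except THIN | hospital discharge diagnoses, all patients |
| 9.3.7, closing rule | no free text, or discharge diagnoses only | hospital discharge diagnoses |
| 9.3.7, sample | those with primary care diagnoses | manual review of about 200 patients |
| Abstract, Limitations | all populations | diagnoses around the prescription date; review in UK and possibly Germany |
| 9.9 | all except THIN | diagnosis codes and medication use before and at start date |

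By Table 9, the 9.3.7 sample rule takes in IACS, SIDIAP and GePaRD as well as THIN. The closing rule of the same section sends those three databases to discharge codes. The two cannot both be the full rule.

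**2. One user followed through the text**

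Take a SIDIAP user with intermittent claudication (I73.9 in Table 4) coded in primary care and a stroke coded at a hospital discharge.

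- Analysis Table 8 (sections 9.3.3 and 9.7.2, primary care and hospital codes): counted as having claudication.
- Analysis Table 21 under the discharge rule: no labelled code is seen, the stroke code is seen, and the user is potentially off-label.
- Analysis Table 21 under section 9.9 or the Abstract's Limitations: the primary care code can be seen if it falls in the period used, and the user is on-label.

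Without the stroke discharge code, the same user has no indication under the discharge rule.

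**3. How many users are in the affected databases**

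Table 10 gives SIDIAP 3,375, THIN 1,640, Sweden 1,800 to 2,200, GePaRD 4,867 to 9,735, and IACS pending. The protocol's own total reproduces:

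- low: 3,375 + 4,867 + 1,640 + 1,800 = 11,682
- high: 3,375 + 9,735 + 1,640 + 2,200 = 16,950

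This agrees with the stated range of about 11,000 to 17,000. Section 9.4.2 later puts GePaRD at about 4,000 users from the two participating insurers. With that figure:

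- SIDIAP + GePaRD = 3,375 + 4,000 = 7,375
- all known users = 7,375 + 1,640 + 1,800 = 10,815, or with 2,200 for Sweden, 11,215
- share = 7,375 / 11,215 = 65.8% to 7,375 / 10,815 = 68.2%

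With Table 10's GePaRD range the share is 68% to 79%. IACS would add to it. Sweden is not counted in the numerator, although its hospital-outpatient codes are also left unused by the discharge rule.

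**4. How much could be lost (assumption only)**

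The documents do not say what fraction of on-label users carry a labelled discharge code. Assume that 90% of users are truly on-label and that discharge codes capture a fraction *s* of them. The share of all users who are on-label but without a labelled code is 0.90 × (1 − *s*):

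- *s* = 0.20: 0.90 × 0.80 = 72%
- *s* = 0.95: 0.90 × 0.05 = 4.5%

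The range is too wide to be an estimate. It shows only that the size depends on a figure the documents do not give.

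**5. Precision table**

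Table 11, which covers off-label use, is sound. Exact (Clopper-Pearson) intervals reproduce 24 of its 25 entries. The exception, 1,500 users at 10%, has a lower bound of 8.5 against the printed 8.6. These intervals describe sampling error and say nothing about the problem here.

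**The case against.** The strongest reply is that the protocol does not uniformly prescribe discharge codes. Section 9.3.7 opens by tying the assessment to the data each database holds, and the sample, the Abstract's Limitations paragraph and section 9.9 all point beyond the hospital. That stands. A reader might infer that on-label outpatient claudication *will* be missed. The documents support this only if the discharge sentences are followed literally, and they do not say which rule was followed.

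A reader might also infer that every user with a cardiovascular admission would be scored off-label. The text does not support that. Section 9.3.7 considers off-label candidates where labelled indications are absent and names only some conditions. An admission can itself carry a claudication code, and many users without a relevant discharge code would be unknown, not off-label.

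Primary care claudication is also not lost to the study, because Analysis Table 8 reports it, so a reader could set the two tables against each other. That mitigates the problem in aggregate but does not correct the classification in Table 21.

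Finally, this is a descriptive secondary objective, the lack of direct indication data is disclosed, and comparability with THIN is limited anyway because only THIN has free text. All true. None of it explains leaving unused codes that the study already needs for Table 8, or stating several rules for one variable.

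**Conclusion.** The point holds as a conflict between passages with a conditional bias. The Abstract and section 9.3.7 fix hospital discharge diagnoses as the source for databases without free text, while other passages of the same protocol state different rules. Applied as written, the discharge rule overstates unknown indication. It also overstates off-label use among users who have an alternative indication coded at discharge.

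The direction follows from the definitions. The amount cannot be calculated from the documents, and the 4.5% to 72% range rests on assumed capture and on-label rates. The 66% to 68% is the share of known users in SIDIAP and GePaRD, not the share misclassified. It uses the approximate GePaRD figure of 4,000 and excludes IACS. If analysts already use all coded diagnoses, the bias disappears, but the Abstract and section 9.3.7 then misstate the method and still need correction.

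**What to change.** Reconcile the Abstract (Variables and Limitations), section 9.3.7 and section 9.9 to one rule per database:

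- **IACS, SIDIAP, GePaRD:** all coded diagnoses, primary care or ambulatory plus hospital.
- **Sweden:** inpatient plus hospital-outpatient diagnoses.
- **Window:** one fixed period around the start date, the same in every database.
- **Classification:** on-label if any labelled code is present; off-label only if none is present and an alternative indication is coded; otherwise indeterminate, reported separately with its own percentage.
- **Manual review:** state which databases the sample of about 200 covers.

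Apply the same rule to DUS1 and DUS2. By section 6.1, DUS1 was complete in THIN, IACS, SIDIAP and Sweden by January 2015. Where discharge codes alone were used there, DUS1 Analysis Table 21 must be rerun, because changing DUS2 alone would break the before/after comparison.

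The cost is protocol wording and modest extra analysis, in more than one database if DUS1 is affected. The protocol already requires these diagnoses for Analysis Table 8, so no new data source is needed.

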### **9.3.8 Assessment of Hospitalisations During Treatment With Cilostazol**

Users of cilostazol will be followed to assess the proportion of users who are hospitalised for any cause during consecutive use of cilostazol. For the THIN database, hospitalisations will be assessed through the hospital diagnoses recorded by GPs. It should be noted that the date of hospitalisation recorded by GPs may not reflect the exact date of hospital admission. This can lead to some misclassification.

### **9.3.9 Speciality of Prescribers**

The type of prescriber initiating treatment with cilostazol will be ascertained in the databases that have this information available: IACS, SIDIAP, GePaRD, Sweden. THIN captures prescriptions only from general practitioners. Type of prescriber will include the following specialities: general practitioner, cardiologist, vascular surgeon, endocrinologist, and other specialities.

## **9.4 Data Sources**

To investigate the use of cilostazol, the DUS requires an efficient means to identify large numbers of users of this drug. At present, the largest and most readily accessible drug utilisation data come from automated databases that record prescriptions, diagnoses, and procedures on an individual-patient basis. Such databases accumulate records longitudinally so that patient experience can be observed before and after prescription of a drug of interest.

Based on usage and reimbursement of cilostazol in European countries with population-based databases, we plan to conduct the DUS in five population-based automated health databases from four European countries:

- The Aragón Health Sciences Institute (Instituto Aragonés de Ciencias de la Salud [IACS]) database in Aragón, Spain

- The Information System for the Advancement of Research in Primary Care (Sistema d'Informació per el Desenvolupament de la Investigació en Atenció Primària [SIDIAP]) database in Catalonia, Spain
- The German Pharmacoepidemiological Research Database (GePaRD ), Germany
- The Health Improvement Network (THIN), United Kingdom
- The Swedish National Databases

#### 9.4.1 Status of Contacts With the Study Databases

Contacts with the database researchers to explore interest in and availability for conducting this study are ongoing. The status in each database is listed in Table 8.

**Table 8. Status in Each Database**

Database	Shared Study Protocol Synopsis	Interest in Participating
IACS, Spain	Yes	Confirmed
SIDIAP, Spain	Yes	Confirmed
THIN, UK	Yes	Agreed to provide the data a
GePaRD, Germany	Yes	Confirmed
National Databases, Sweden	Yes	Confirmed

a After scientific committee approval and registration of the study in ENCePP. The THIN Scientific Review Committee approved the study in February, 2013.

#### 9.4.2 Description of Databases

The characteristics of the study databases in Spain, Germany, the UK, and Sweden are summarised in this section and also in Table 9 at the end of this section.

##### Spain

*Aragón:* A group of researchers in Public Health and Health Services Research of the Aragón Health Sciences Institute (Instituto Aragonés de Ciencias de la Salud [IACS]) has linked the electronic medical and administrative databases in the region. These databases contain administrative and clinical information from outpatient clinics (primary care health centres), specialty clinics, emergency departments, hospitals, and pharmacies. From 2010 onwards, data are available for 1.2 million patients covered by all outpatient practices in Aragón. The following types of data are available: administrative and clinical information from outpatient clinics (primary care health centres), administrative and clinical information from specialty clinics, emergency department diagnoses and care, hospital procedures and discharge diagnoses, and pharmacy prescription data.

Studies are conducted in collaboration with the Institute of Public Health and Health Services Research; ethics committee approval is needed for the study. The principal investigator in IACS will be [name] [name].

*Catalonia:* The Information System for the Advancement of Research in Primary Care (SIDIAP) currently collects information from 274 primary health care centres, including more than 5.8 million patients, about 80% of the Catalan population covered by the Catalan Institute of Health (Bolíbar et al., 2012). Primary care physicians with an up-to-standard quality of care provide information on approximately 1.9 million patients (García-Gil et al., 2011). Information from different data sources can be accessed through linkage by an individual's national security number, including demographic information from the Catalan Health Services database, electronic primary care clinical and laboratory test records, drugs dispensed in community pharmacies, hospital discharge codes from an external database on hospital admissions (CMBD-AH), date and cause of death from the National Office of Statistics, and other available disease or procedural registries. The current primary care database includes data from the year 2000 through April 2012; however, the start of data availability of elements from other linkable data sources varies from 2003 for mortality data to 2006 for laboratory data. Availability of pharmacy dispensed drug information is available since 2005.

Studies are conducted in collaboration with the Institute of Research in Primary Health Care; ethics committee approval is needed for the study.

